## **Time to return to normal health and activity**

Time to return to normal health and activity will be summarized using descriptive statistics by treatment, as well as Kaplan-Meier plots.

‘Normal health and activity’ is identified by a ‘Yes’ response to the following question on the CARIFS: “Since the last assessment has the patient been able to return to day care/school, or resume his or her normal daily activity in the same way as performed prior to developing the flu?”

Patients who do not return to normal health and activity will be censored at the last observation time point.

## **Frequency of influenza-related complications**

The number of influenza-related complications, as well as the number and percentage of patient with these complications, after treatment, will be presented by treatment. Influenza-related complications include death, hospitalization, radiologically-confirmed pneumonia, bronchitis, sinusitis, otitis media, encephalitis/encephalopathy, febrile seizures and myositis, as recorded on the AE pages of eCRF.

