### **1.3 STUDY RATIONALE AND BENEFIT-RISK ASSESSMENT**

Influenza virus infection predisposes to secondary bacterial infection, which may progress in severity leading to poor prognosis, particularly in children. Other serious complications can also develop, including cardiac and neurological complications.

Although NA inhibitors, such as oseltamivir, zanamivir, and peramivir, can be used for the treatment of pediatric patients at present, more convenient and potent anti-influenza virus drugs without restriction of use are needed for the following reasons: 1) zanamivir is not licensed for treatment of influenza in very young children due to the difficulty with inhalation in this group (<5 or 7 years of age, depending on country), 2) peramivir needs to be intravenously administered, and 3) oseltamivir requires BID dosing orally for 5 days.

The efficacy of currently marketed antivirals against preventing complications in pediatric patients has not been demonstrated. Baloxavir marboxil appears to have greater antiviral efficacy compared with currently available antivirals, offering the potential to treat influenza in the pediatric population more effectively.

A new antiviral drug against influenza is needed with a novel mode of action to overcome potential resistance to existing antivirals or offer a different resistance profile.

The results of the clinical studies outlined above have proven the efficacy and safety of baloxavir marboxil in the treatment of influenza virus infections for adult and adolescent patients. Although limited clinical data is available in children (one open-label Phase III

study in children in Japan), an active-controlled study of children is justified to confirm the safety, pharmacokinetics, and efficacy of baloxavir marboxil in the pediatric population.

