**Table 1 Objectives and Corresponding Endpoints (cont.)**

Efficacy (Secondary) Objectives	Corresponding Endpoints

 
To evaluate the clinical efficacy of baloxavir marboxil compared with oseltamivir
 
	
 
Duration of fever (time to return to afebrile state [tympenic temperature <math>\leq 37.2^{\circ}\text{C}</math>] and remaining so for at least 21.5 hours)
 
Duration of symptoms (alleviation of all symptoms as defined by a score of 0 [no problem] or 1 [minor problem] and remaining so for at least 21.5 hours, for all 18 symptoms specified in the CARIFS questionnaire)
 
Time to return to normal health and activity
 
Frequency of influenza-related complications (death, hospitalization, radiologically confirmed pneumonia, bronchitis, sinusitis, otitis media, encephalitis/encephalopathy, febrile seizures, myositis)
 
Proportion of patients requiring antibiotics
 

Secondary Virology Objective	Corresponding Endpoints

 
To evaluate the virological activity of baloxavir marboxil compared with oseltamivir
 
	
 
Time to cessation of viral shedding by virus titer and by RT-PCR
 
Change from baseline in influenza virus titer and in the amount of virus RNA (RT-PCR) at each time point
 
Proportion of patients with positive influenza virus titer and proportion of patients positive by RT-PCR at each time point
 
Area under the curve in virus titer and in the amount of virus RNA (RT-PCR)
 

Exploratory Objectives	Corresponding Endpoints

 
To evaluate the polymorphic and treatment-emergent amino acid substitutions in the PA, PB1, and PB2 genes and drug susceptibility in patients with evaluable virus
 
To evaluate extended PK parameters of baloxavir marboxil after single-dose administration
 
	
 
Polymorphic and treatment-emergent amino acid substitutions in the PA, PB1, and PB2 genes
 
Drug susceptibility in patients with evaluable virus
 
Non-compartmental PK parameters (intensive PK)
 

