### **5.2.1 Adverse Events**

According to the ICH guideline for Good Clinical Practice, an adverse event is any untoward medical occurrence in a clinical investigation patient administered a pharmaceutical product, regardless of causal attribution. An adverse event can therefore be any of the following:

- Any unfavorable and unintended sign (including an abnormal laboratory finding), symptom, or disease temporally associated with the use of a medicinal product, whether or not considered related to the medicinal product
- Any new disease or exacerbation of an existing disease (a worsening in the character, frequency, or severity of a known condition) (see Section 5.3.5.8 and Section 5.3.5.9 for more information)
- Recurrence of an intermittent medical condition (e.g., headache) not present at baseline
- Any deterioration in a laboratory value or other clinical test (e.g., ECG, X-ray) that is associated with symptoms or leads to a change in study treatment or concomitant treatment or discontinuation from study drug
- Adverse events that are related to a protocol-mandated intervention, including those that occur prior to assignment of study treatment (e.g., screening invasive procedures such as biopsies)

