#### **5.3.5.9 Lack of Efficacy or Worsening of Influenza**

Medical occurrences or symptoms of deterioration that are anticipated as part of influenza, such as fluctuation in symptoms, should only be recorded as an adverse event if judged by the investigator to have unexpectedly worsened in severity or frequency or changed in nature at any time during the study. When recording an unanticipated worsening of influenza on the Adverse Event eCRF, it is important to convey the concept that the condition has changed by including applicable descriptors (e.g., "accelerated worsening of influenza").

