## **5.7 EXPEDITED REPORTING TO HEALTH AUTHORITIES, INVESTIGATORS, INSTITUTIONAL REVIEW BOARDS, AND ETHICS COMMITTEES**

The Sponsor will promptly evaluate all serious adverse events and adverse events of special interest against cumulative product experience to identify and expeditiously communicate possible new safety findings to investigators, IRBs, ECs, and applicable health authorities based on applicable legislation.

To determine reporting requirements for single adverse event cases, the Sponsor will assess the expectedness of these events using the following reference documents:

- Baloxavir Marboxil Investigator's Brochure
- Tamiflu® local prescribing information

The Sponsor will compare the severity of each event and the cumulative event frequency reported for the study with the severity and frequency reported in the applicable reference document.

Reporting requirements will also be based on the investigator's assessment of causality and seriousness, with allowance for upgrading by the Sponsor as needed.

An IMC will monitor the incidence of the above-listed anticipated events during the study. An aggregate report of any clinically relevant imbalances that do not favor the test product will be submitted to health authorities in countries where the study is being conducted, within adverse event/serious adverse event reporting timelines upon the Sponsor being informed by the IMC.

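### Influenza complications are counted from the AE pages alone, but the protocol leaves AE entry of non-serious complications to investigator judgment

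*SAP*

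**What the plan says.** Protocol Table 1 makes the complications a secondary efficacy endpoint: "Frequency of influenza-related complications (death, hospitalization, radiologically confirmed pneumonia, bronchitis, sinusitis, otitis media", followed by encephalitis or encephalopathy, febrile seizures and myositis. The protocol names no data source for it. SAP 4.6.1 does, closing the same list with "febrile seizures and myositis, as recorded on the AE pages of eCRF". Neither document names another source, a dedicated form or a set of preferred terms.

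Protocol 5.3.5.9 sets a condition on what reaches those pages. It covers "Medical occurrences or symptoms of deterioration that are anticipated as part of influenza, such as fluctuation in symptoms", which "should only be recorded as an adverse event if judged by the investigator to have unexpectedly worsened in severity or frequency or changed in nature".

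Other rules bear on the same events:
- Protocol 5.2.1 counts as an adverse event "Any new disease or exacerbation of an existing disease", but that bullet sends the reader on to 5.3.5.8 and 5.3.5.9.
- Protocol 5.3.5.2 generally identifies secondary events by their primary cause unless they are severe or serious. It also asks for a separate entry when a medically significant secondary event is separated in time, or when the association is unclear.
- Protocol 5.3.5.7 puts every death in the reporting period on the AE eCRF, including deaths from influenza.
- Protocol 5.3.5.10 makes an adverse event that leads to hospitalization a serious adverse event, apart from respite and certain planned admissions.

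Protocol 5.7 adds: "An IMC will monitor the incidence of the above-listed anticipated events during the study". No such list appears above that sentence.

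**The concern.** The endpoint can count only what sites enter as adverse events, and the entry rule turns on whether an occurrence is anticipated as part of influenza. The protocol does not say on which side of that line the listed complications fall. Its own background gives an investigator reason to regard some as anticipated: Section 1.3 says "Influenza virus infection predisposes to secondary bacterial infection" and mentions neurological complications, and Section 1.1 singles out young children as at particular risk of secondary bacterial infection.

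Two investigators who both follow the protocol could therefore treat the same mild otitis media differently. One enters it as a new diagnosis. The other leaves it off as part of the expected course. The secondary endpoint would then partly reflect recording habits, and the AE incidence in the primary safety objective would miss the same events.

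**Working it through.** **1. The rules applied to each component.**

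| Component | Rule that secures entry | Remaining gap |
|---|---|---|
| Death | 5.3.5.7, all deaths | None of substance |
| Hospitalization | 5.3.5.10, when it results from an AE | Small; depends on the cause being accepted as an AE |
| Pneumonia, encephalitis/encephalopathy | Serious-event rules, where serious | Small when serious |
| Bronchitis, sinusitis, otitis media, myositis, possibly a brief febrile seizure | 5.2.1, new disease | Open: 5.2.1 refers to 5.3.5.9, and 5.3.5.2 may also apply |

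The exposure is mainly in the last row. If a site treats influenza as the primary cause under 5.3.5.2, influenza is the entry condition and need not itself be an AE entry, so the complication could leave no trace on the AE pages.

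**2. Spread over sites.** Protocol 9.4 plans about 120 patients at about 75 sites: 120 / 75 = 1.6 children per site. Differences in reading the rule therefore become differences between patients.

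**3. The plan's own detection figures.** Protocol Table 4 (SAP Table 1) gives the chance of at least one case among 80 patients, P = 1 − (1 − p)^80.

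| True incidence p | 1% | 2% | 3% | 4% | 5% |
|---|---|---|---|---|---|
| Stated | 55.2% | 80.1% | 91.3% | 96.2% | 98.3% |
| Recomputed | 55.25% | 80.14% | 91.26% | 96.18% | 98.35% |

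The table reproduces, and nothing in it is wrong on this point.

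**4. Illustration of under-recording.** The documents give neither a complication rate nor the share q that would be entered, so both are assumptions. Expected counts are 80·p·q and 40·p·q. The chance of at least one recorded case among 80 is 1 − (1 − p·q)^80.

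| Assumed p | q | Expected (80 / 40) | P(at least 1 of 80) |
|---|---|---|---|
| 3% | 100% | 2.4 / 1.2 | 91.3% |
| 3% | 75% | 1.8 / 0.9 | 83.8% |
| 3% | 50% | 1.2 / 0.6 | 70.2% |
| 5% | 100% | 4.0 / 2.0 | 98.3% |
| 5% | 75% | 3.0 / 1.5 | 95.3% |
| 5% | 50% | 2.0 / 1.0 | 86.8% |
| 10% | 100% | 8.0 / 4.0 | above 99.9% |
| 10% | 50% | 4.0 / 2.0 | 98.3% |

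For a 3% event with one case in three omitted, p·q = 0.03 × 2/3 = 2%. The chance falls from 91.3% to 80.1%, below the 90% aim in Protocol 6.2. Efficacy is summarized in the ITTi population, a subset of ITT, so actual counts may be smaller.

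**5. Effect on the comparison.** With the same q in both arms, the recorded ratio is (q·p1)/(q·p2) = p1/p2, which is unchanged. The recorded difference is q·(p1 − p2), which shrinks with q. Precision falls too. The standard error of the log ratio is √(1/4 − 1/80 + 1/2 − 1/40) = 0.84 for 4/80 against 2/40, and √(1/2 − 1/80 + 1/1 − 1/40) = 1.21 for 2/80 against 1/40. This approximation is rough at such counts and serves only to show direction.

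**The case against.** A reader might infer that 5.3.5.9 forbids recording complications. The text does not support that. The rule is conditional, its only example is symptom fluctuation, and it names none of the listed diagnoses. A new otitis media can fairly be read as a change in nature, or as a new disease under 5.2.1. Section 4.5.3 asks that new clinically significant examination findings be recorded as adverse events, and 5.3.5.1 prefers a diagnosis to its symptoms. In the earlier Phase III study in adults and adolescents, bronchitis and sinusitis did appear among the reported adverse events (Protocol 1.2.2). Section 7.2 promises training and an eCRF manual, which is not public and may settle the matter.

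Most of this stands: it makes loss less likely and shows that none has been demonstrated. It does not close the gap. The example in 5.3.5.9 is not exhaustive, 5.2.1 refers back to that section, clinical significance is again a judgment, and the earlier study's recording rule is not given.

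Two other inferences also go too far. One is that a treatment difference would be diluted in general. Site staff and patients are blinded with matching placebos, so differential capture is unlikely and the ratio is preserved in expectation. The other is that the Internal Monitoring Committee lacks an event list and complete data. Its charter is not public, so only the unresolved reference in 5.7 can be shown. The one section missing from the public text nearby is 5.4.1, emergency contacts, which would not be expected to hold such a list.

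**Conclusion.** The point holds as an inconsistency between a stated data source and a stated recording rule. Non-serious bronchitis, sinusitis, otitis media, myositis and possibly febrile seizures can be recorded inconsistently and under-counted in a descriptive secondary endpoint and in AE incidence. Deaths are secured, and AE-related hospitalizations largely so.

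The size of any loss cannot be computed from the documents; the rates and capture shares above are assumptions. If capture is similar in the two arms, as blinding makes likely, the consequence is lower counts, a smaller absolute difference and less precision, without bias in the expected ratio. No hypothesis test is affected because none is planned. The missing list in 5.7 is a separate, smaller defect. Overall this is a cheap improvement and does not threaten the trial's conclusions.

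**What to change.** Add to Protocol 5.3.5.9, with a cross-reference in 5.3.5.2, and repeat in the eCRF guide:

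*A new diagnosis of otitis media, sinusitis, bronchitis, radiologically confirmed pneumonia, myositis, febrile seizure or encephalitis/encephalopathy after the start of treatment is always entered on the Adverse Event eCRF, whether or not it is anticipated as part of influenza. Deaths and hospitalizations are recorded according to 5.3.5.7 and 5.3.5.10.*

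Death and hospitalization are left out of the blanket requirement on purpose. Section 5.3.5.7 treats death as an outcome of an event, and 5.3.5.10 exempts some admissions, so including them would create new contradictions.

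Separately, the sponsor should insert the intended list of anticipated events in 5.7 or point to the committee's charter. It should not be assumed to be the Table 1 list.

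The cost is a protocol clarification, a site memo and a slightly higher AE count in both arms. Treatment and visits do not change.

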## **Proportion of patients requiring antibiotics**

The number and percentage of patients requiring antibiotics for any reason will be presented by treatment group.

## **4.6.2 Virology (Secondary) Endpoints**

### **Time to cessation of viral shedding by virus titer**

Time to cessation of viral shedding by virus titer is defined as the time, in hours, between the initiation of any study treatment and first time when the influenza virus titer is below the limit of detection. Patients whose virus titers have not reached the limit by the last observation time point will be treated as censored at that time point. One day is converted into 24 hours.

Patients with a positive virus titer on Day 1 will be included in this analysis.

This endpoint will be summarized using descriptive statistics by treatment, as well as Kaplan-Meier plots.

### **Time to cessation of viral shedding by RT-PCR**

Time to cessation of viral shedding by RT-PCR, in hours, is defined as the time between the initiation of any study treatment and first time when the virus RNA by RT-PCR is below the limit of detection. Patients whose virus RNA have not reached the limit by the last observation time point will be treated as censored at that time point. For the patients with multiple virus types, this endpoint is defined as the time between the initiation of the study treatment and first time when the virus RNA by RT-PCR is below the limit of detection for all virus types. One day is converted into 24 hours.

Patients with a positive virus RNA on Day 1 will be included in this analysis.

This endpoint will be summarized using descriptive statistics by treatment, as well as Kaplan-Meier plots.

### **Change from baseline in influenza virus titer at each time point**

Change from baseline in influenza virus titer ( $\log_{10}$ TCID50/ML) will be presented by treatment and is defined as the change from baseline in influenza virus titer on Days 2, 4, 6, and 10. If influenza virus titer is less than the lower limit of quantification, the virus titer will be imputed as 0.749 ( $\log_{10}$ TCID50/mL).

Only patients with a positive virus titer on Day 1 will be included in this analysis.

### **Change from baseline in the amount of virus RNA (RT-PCR) at each time point**

Change from baseline in the amount of virus RNA (unit:  $\log_{10}$  virus particles/mL) will be presented by treatment and is defined as the change from baseline in the amount of virus RNA on Days 2, 4, 6, and 10.

If the amount of virus RNA is less than the lower limit of quantification, the amount of virus RNA will be imputed as 2.18 for flu A and 2.93 for flu B ( $\log_{10}$  virus particles/mL). If a patient is infected with multiple virus types, the sum of those amounts of virus RNA will be used for analysis.

Patients with a positive by RT-PCR on Day 1 will be included in this analysis.

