### **1.2.3 Phase III Open-Label Study in Otherwise Healthy Pediatric Patients (Study 1618T0822)**

In this Phase III, open-label study in otherwise healthy pediatric patients, the efficacy of a single dose of baloxavir marboxil in patients aged 6 months to < 12 years was investigated. This study was conducted in Japan. A total of 107 patients were enrolled: 2, 31, 66, and 8 patients received a single 5-, 10-, 20-, and 40-mg dose of baloxavir marboxil, respectively. The doses administered in this study were 5, 10, 20, and 40 mg for patients who weighed 5 to < 10 kg, 10 to < 20 kg, 20 to < 40 kg, and  $\geq$  40 kg, respectively.

The median time to alleviation of influenza illness (time to alleviation of cough, nasal discharge/nasal congestion, and fever) was 44.6 hours. Of the secondary endpoints, the median time to resolution of fever was 21.4 hours. In the virological endpoints, the mean change from baseline in the virus titer was  $-4.20 \log_{10}$  (TCID50/mL) and the mean change from baseline in the amount of viral RNA was  $-1.75 \log_{10}$  (virus particles/mL) on Day 2.

No deaths, serious adverse events, or discontinuations due to adverse events were reported in the study. Adverse events were reported in 37 of 107 patients (34.6%, 49 events). All adverse events were classified as Grade 1 or 2. Most of the adverse events resolved except for 3 adverse events in 3 patients: 1 event each of dental caries, dry skin, and ligament sprain (these were judged by the investigator to not require further follow-up).

Adverse events occurring at an incidence of at least 5% was vomiting in 8 patients (7.5%, 8 events). All the cases of vomiting were classified as Grade 1, resolved, and considered not related to the study drug.

Baloxavir marboxil was considered generally safe when administered to pediatric patients with influenza at a single oral dose between 5 mg and 40 mg based on the patient's body weight.

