#### **4.6 EFFICACY ANALYSIS**

The statistical analyses of efficacy endpoints will be descriptive. The ITTi population will be used for all analyses. Additional analysis of efficacy analysis presenting the ITT population will not be completed.

The data will be summarized using means, standard deviations, medians, and ranges for continuous variables and proportions for categorical variables, as appropriate. Time-to-event endpoints and duration endpoints will be summarized using Kaplan-Meier plots and summaries of the median survival time. Summaries will be presented by treatment group.

Efficacy endpoints are based on the CARIFS questionnaire data which is recorded by parent/ caregiver using handheld device. This assessment data should be recorded for the following time periods:

Period	Time
Morning	0.500-10.59
Noon	11.00-14.59
Evening	15.00-18.59
Bedtime	19.00-23.59

\*data should not be recorded between 00.00 and 4.59.

In the case where the recorded time of an assessment is outside the period time window for that assessment, the end time of the period should be imputed as the assessment time.

In the case where the assessment time falls into the period between 00.00 and 4.59 (due to technical error) the assessment date will be imputed to the date prior to recorded assessment date and the assessment time will be imputed to the end time of the period time window.

The imputation method used in the derivation of time to alleviation of influenza signs and symptoms is described in Section 4.6.1. No further imputation methods will be used.

In all time to event analysis, patients who withdraw prior to event of interest will be censored at the last observation timepoint.

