### **Area under the curve in virus titer**

Area under the curve (AUC) in virus titer will be presented by treatment group and will be calculated using the trapezoidal method. AUC of change from time 0 ( $t_0$ ) to time K ( $t_k$ ) is given by the formula

$$\sum_{k=1}^K \frac{(y_k + y_{k-1} - 2y_0)(t_k - t_{k-1})}{2}$$

where  $t_k$  (hours) represents the date of the  $k^{\text{th}}$  viral titer assessment ( $k = 0, \dots, K$ ) and  $y_k$  represents the  $\log_{10}$  value of the  $k^{\text{th}}$  viral titer assessment ( $\text{TCID}_{50}/\text{mL}$ ).

24-hours of time will be converted into one day. Patients with a positive virus titer on Day 1 will be subjected to this analysis. The lower limit is defined as  $0.75 \log_{10} \text{TCID}_{50}/\text{mL}$  for flu A and  $0.75 \log_{10} \text{TCID}_{50}/\text{mL}$  for flu B ( $\text{TCID}_{50}/\text{mL}$ ). If a patient is infected with multiple virus types, the sum of those virus titers will be used for analysis.

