### **Area under the curve in the amount of virus RNA (RT-PCR)**

AUC in virus RNA (RT-PCR) will be presented by treatment group and is defined as AUC of change from baseline in the amount of virus RNA (RT-PCR) from Day 1 to Day 10. AUC is calculated using the trapezoidal method similar to AUC in virus titer. Patients with a positive RT-PCR result on Day 1 will be subjected to this analysis. The lower limit of quantification is defined as  $2.18$  for flu A and  $2.93$  for flu B ( $\log_{10}$  virus particles/mL). If a patient is infected with multiple virus types, the sum of those the amount of virus RNA will be used for analysis.

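### For children infected with more than one virus type, the SAP defines the RNA amount in log10 units and then sums it; read literally, the rule adds logs and overstates the fall in load.

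*SAP*

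**What the plan says.** SAP section 4.6.2 has a rule for multiple virus types in three quantitative virology paragraphs.

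- **RNA change from baseline.** The endpoint is given with "unit: $\log_{10}$ virus particles/mL". Below LLOQ, "the amount of virus RNA will be imputed as 2.18 for flu A and 2.93 for flu B", on the same log10 scale. For a child with several types, "the sum of those amounts of virus RNA will be used for analysis".
- **RNA AUC.** The LLOQs are again 2.18 and 2.93 in log10 units, and "the sum of those the amount of virus RNA will be used for analysis".
- **Titer AUC.** In the formula, y is the log10 value of a titer assessment in TCID50/mL, and the lower limit is 0.75 log10 for each type. For several types, "the sum of those virus titers will be used for analysis".

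None of the three paragraphs mentions back-transformation. The paragraph on time to cessation of shedding by RT-PCR also covers multiple types but takes no sum: it requires every type to be below the limit of detection. The paragraph on change in titer has no multiple-type rule.

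**The concern.** In the RNA change paragraph, the quantity to be summed is one that the text has just defined and imputed in log10. A programmer who follows the sentence as it stands adds 2.18 to 2.93. A sum of logs is the log of the product of the two loads, not the log of the total load, and the error does not cancel on subtracting baseline, because the falls in the two types are added together.

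Two analysts could each claim to follow the SAP and report different values for the same child. The difference would enter the mean RNA change at Days 2, 4, 6 and 10, the RNA AUC and possibly the titer AUC. The arms are small, and a few such children, unevenly split, could visibly move a descriptive comparison.

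**Working it through.** The plan states no figure for this rule, so there is none to reproduce. The check compares the two scales on which the sum could be taken.

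**Inputs from the documents**
- Values imputed below LLOQ (SAP 4.6.2, RNA change): 2.18 log10 for flu A and 2.93 log10 for flu B.
- Planned arm sizes (SAP 2.3): 80 and 40.
- An illustrative fall (Protocol 1.2.3): on Day 2, "the mean change from baseline in the amount of viral RNA was" −1.75 log10.

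**Assumptions (not in the documents)**
- Baseline load of about 3 to 7 log10 per type.
- The follow-up values in the table, other than the floors.
- The number of co-infected children.

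**Formulas**, with a and b the log10 values for the two types, 0 = baseline and 1 = follow-up:
- Sum of logs: (a1 + b1) − (a0 + b0)
- Log of the summed load: log10(10^a1 + 10^b1) − log10(10^a0 + 10^b0)

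**Floor**, both types below LLOQ:
- Sum of logs: 2.18 + 2.93 = 5.11, which is about 129,000 particles/mL.
- Log of the summed load: log10(151 + 851) = log10(1,002) = 3.00.

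**Worked change from baseline**, 6 and 5 log10 falling to the floors:
- Sum of logs: 5.11 − 11 = −5.89
- Log of the summed load: 3.00 − log10(1,100,000) = 3.00 − 6.04 = −3.04
- Ratio 1.94; difference 2.85 log10.

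**Other assumed loads**

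| Baseline (a/b) | Follow-up (a/b) | Sum of logs | Log of summed load | Ratio |
|---|---|---|---|---|
| 7 / 7 | 2.18 / 2.93 | −8.89 | −4.30 | 2.07 |
| 5 / 5 | 2.18 / 2.93 | −4.89 | −2.30 | 2.13 |
| 7 / 5 | 2.18 / 2.93 | −6.89 | −4.00 | 1.72 |
| 7 / 4 | 2.18 / 2.93 | −5.89 | −4.00 | 1.47 |
| 7 / 3.2 | 2.18 / 2.93 | −5.09 | −4.00 | 1.27 |
| 7 / 7 | 5.25 / 5.25 (each −1.75) | −3.50 | −1.75 | 2.00 |
| 7 / 3.2 | 5.25 / 2.93 | −2.02 | −1.75 | 1.16 |
| 7 / 7 | 5 / 7 (one type falls) | −2.00 | −0.30 | 6.74 |

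When the two types fall by similar amounts the ratio is about 2. It is nearer 1.2 when the second type starts low. It is much larger when one type falls and an equal load of the other persists.

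**AUC**, using the SAP's trapezoid Σ(y_k + y_{k−1} − 2y_0)(t_k − t_{k−1})/2 at 0, 24, 72, 120 and 216 hours. Assumed curves are 7, 5.25, 4, 3 and then the floor, for both types.
- Sum of logs (14, 10.5, 8, 6, 5.11): −42 − 228 − 336 − 810.72 = −1,416.7 log10·h
- Log of the summed load (7.30, 5.55, 4.30, 3.30, 3.00): −21 − 114 − 168 − 398.4 = −701.4 log10·h
- Ratio 2.02.

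**Effect on an arm mean** of one co-infected child is the difference divided by n.
- 6 and 5 to the floors: 2.85/80 = 0.04; 2.85/40 = 0.07 log10.
- 7 and 7 to the floors, difference 8.89 − 4.30 = 4.59: 4.59/80 = 0.06; 4.59/40 = 0.11. Four such children: 0.23 and 0.46.

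The analysis takes only infected children who are RT-PCR positive on Day 1. The true n may therefore be below 80 and 40, and the shift larger in proportion.

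**The case against.** The strongest answer is that the SAP never says that logs are added. An amount of RNA can also mean particles/mL, added first and logged afterwards. **This stands in part.** A reader might infer that the SAP definitely multiplies the loads, and the text does not prove that. But in the RNA paragraphs the only scale given for the amount is log10, and no step returns to the natural scale, so the literal instruction gives the wrong total.

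The titer AUC paragraph is weaker evidence. It defines y as the log10 of a titer in TCID50/mL, so summing titers and then taking the log is a natural reading. A reader might count it as a third instance of the same error; the text shows only that the scale is not stated.

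A reader might also infer that the rule about doubles the decline in general. It does so only when both types fall by similar amounts.

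The reach is narrow, and this stands in full. Only co-infected children are affected, in three summaries. SAP 4.6 says "The statistical analyses of efficacy endpoints will be descriptive", so no test or power statement depends on it.

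Finally, a natural-scale sum is dominated by the larger type: 7/7 falling to 5/7 shows only −0.30 and hides a 2-log fall in one virus. That is true, but it is what a total load means. If the sponsor wants the fall in each virus, it can report the types separately; adding logs gives neither a total nor a result by type.

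**Conclusion.** The rule for RNA change and RNA AUC is wrong as literally written, and the titer AUC rule leaves its scale open. The 5.11 against 3.00 log10 floor follows from the SAP's own values. The inflation of about 1.2 to 2.1 times, and the larger figure when one type persists, rest on assumed loads of about 3 to 7 log10 per type. The shift of 0.04 or 0.07 log10 in an arm mean rests on one child with assumed loads of 6 and 5 log10 and on the planned arm sizes. The documents do not say how many children will have more than one type. If there are none, nothing changes. The endpoints are secondary, so this is a low-priority correction, but a clear one.

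**What to change.** In the RNA change, RNA AUC and titer AUC paragraphs of SAP 4.6.2, state that for a child with more than one virus type each type's value, after LLOQ imputation, is back-transformed, the values are summed on the natural scale, and the sum is log10-transformed before change from baseline or AUC is computed. It would help to state also whether a type not detected at baseline enters the sum.

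The cost is one sentence in each of three paragraphs and a matching line in the programming specification. It needs no new data and leaves results for children with a single type unchanged.
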